Serious adverse events which are considered by site staff or the study sponsor to be potentially cardiovascular in nature will be reviewed to determine whether the event should be considered a major adverse cardiovascular event (MACE) as defined by the CARES trial (CARES appendix s2). Adjudication will be performed independently by at least two experienced cardiologists, with a third adjudicator used to break ties. Each potential cardiovascular SAE will be assigned to one of the following categories.

- Arrhythmias not associated with ischemia
- Cardiovascular Death
- Hospitalization for Heart Failure
- Non-fatal Myocardial Infarction
- Stroke
- Transient Ischemic Attack (TIA)

- Unstable Angina requiring urgent revascularization
- Other cardiac event
- Not a cardiac event

The decision as to whether participants who experience a cardiovascular event should be continued in the protocol is at the discretion of the local site investigator. The study chair should be consulted for any questions or concerns.

Patients reporting skin rash at any time during the study will be evaluated in-person by a study investigator, with structured data collection completed in order to precisely characterize the nature and severity of the rash. Data to be collected pertinent to rashes will include the individual components of the provisional classification criteria for the definition of allopurinol hypersensitivity syndrome (AHS) (81) (see criteria below). We will modify these criteria slightly to include the use of either allopurinol or febuxostat, recognizing that the frequency of rashes for the two drugs has been similar in head-to-head trials conducted to date and serious cutaneous reactions have been reported for febuxostat during post-marketing surveillance. Participants satisfying criteria for drug-related hypersensitivity will discontinue study medication and will be counted as a treatment failure but will continue to be followed. Participants presenting with rashes that do not satisfy these criteria may be continued in the protocol at the discretion of the site investigator and the study chairman. Such participants will have the option of continuing on protocol at stable or reduced doses of study medications at the discretion of the site investigator.

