The results for the primary hypothesis will be analyzed by means of a one-sided 95% confidence interval on the difference in proportion of participants with one or more gout flare events. The test of the difference between proportions will have one-sided type I error of 5%. Starting with a total of 950 participants, allowing 5% dropout, and retaining 900 participants, the test has 90% power to reject the null hypothesis of inferiority with a total of 900 participants, 450 participants per arm,

For large samples, regarding the difference between proportions as the difference between means, the use of the standard Student's t distribution closely approximates the non-central t-distribution and justifies use of the power formula 3.2.4 (in section 3.2.2) below (Chow, Shao, and Wang (86):

$$n = n_1 = n_2 = \frac{(Z_\alpha + Z_\beta)^2 2\sigma^2}{(D - B)^2}$$

Note: $n = 450$ is the number of participants in each of the two study arms, $Z_\alpha = 1.645$ is the cut point for a one-sided test with a 5%, Type I error, $Z_\beta = 1.28$ provides 90% power, Bound = 8%, $D=0\%$ is the true difference between the treatment outcome measures, and $\sigma^2 = 0.16$ is the variance associated with the distribution of for a single Bernoulli observation.

As rates are uncertain, we note that if the Phase 3 rate of gout flares is either 15%, 20%, or 25% then the respective statistical powers are 96%, 91%, and 87%. With a rate of 20%, but a higher dropout rate of 10%, the power is 90%. Non-adherence to treatment, inability to attain $sUA < 6$ mg/dl, or failure to appear for clinic visits will not affect dropout, only the explicit decision of the patient to leave the study. Participants who experience toxicity that either reduced dosage or other medications reduce to a tolerable level can remain on study if they wish to do so.

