In this study all patients will return to standard care – in some cases this will be primary care providers and in other cases this will be rheumatologists specifically for gout related follow-up. At the end of the study (week 72) the participant will return for their final study visit and the LSI and SC will inform the participant of the study drug that they have been taking. In addition, the study team will send a letter to the treating physician and if applicable, a CPRS note will be completed. Treatment decisions after the study will be up to the primary care doctor's discretion. For participants who choose to withdraw from the study early or have been lost to follow-up (who received drug and have neither revoked consent or HIPAA authorization) the study team will unblind them at what would have been their expected week 72 visit via a letter to their PCP and a note in CPRS. If at any point during the study a subject passes away, the unblinding process listed above is not required. Since gout is a major part of the metabolic syndrome which has a marked increase and morbidity and mortality, particularly from cardiovascular events a 10-year passive follow-up will provide extremely valuable insights in how long-term control of hyperuricemia modifies risks for cardiovascular events, hypertension and renal failure. The 10-year passive follow-up is being sought to explore the impact of improved gout management on long term effects related to gouty arthritis/disability and progression of renal and cardiovascular disease (refer to page 8, section titled "Other Objectives" for a detailed outline). This follow-up will only be in VA patients and will explore meaningful clinical outcomes such as dialysis, MI, stroke and death which are resident in the electronic health record.

Schedule of Events:

A schedule for all study-related procedures including ULT clinic visits, telephone contacts, and laboratory surveillance are shown in the table below:

Table 5: Study follow-up and procedures¹

	SC ²	Phase 1 – Dose Titration										Phase 2 – Optimization and Maintenance				Phase 3 – Steady State Flare Observation			
		0	3	6	9	12	15	18	21	24	30 ³	36	42 ³	48 ⁴	Every 4 weeks	Week 60	Every 4 weeks	72 ⁴	
Informed Consent	X																		
ULT Clinic visit	X	X		X		X		X		X		X		X		X		X	
Telephone contact			X		X		X		X		X		X		X		X		
Gout Flare ⁵				X		X		X		X		X		X		X		X	
sUA blood draw	X	X		X	†	X	†	X	†	X	X	X	X	X		X		X	
Creatinine	X	X		X		X		X		X		X		X		X		X	

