SAEs are a subset of adverse events. As defined in VHA Handbook 1058.01, a serious adverse event (SAE) is an untoward occurrence in human research that results in:

- Death
- A life-threatening experience
- Inpatient hospitalization
- Prolongation of hospitalization
- Persistent or significant disability or incapacity
- Congenital anomaly or birth defect, or
- Requires medical, surgical, behavioral, social or other intervention to prevent such an outcome

All SAEs will be collected and reported via DataLabs and to CSPCRPCC and MAVERIC CSPCC within 3 calendar days of knowledge, regardless of whether or not they are considered related to the study interventions. SAEs with a reasonable causal relationship to the study interventions and associated medications will be reported as “possibly related” or “related.” A definite causal relationship does not need to be established.

While additional evidence about febuxostat’s cardiovascular risks continues to accumulate, side effect profiles for both study medications (allopurinol and febuxostat) and all the supplemental medications (prednisone, colchicine and naproxen) are generally well established and will be used as the basis to determine what are expected and unexpected events. Local site investigators will determine the relatedness to the study medications for any reported event. These local site investigators, with assistance from their study coordinators, are responsible for collecting SAE information regarding the participants at their sites. SAEs will be collected from the time of consent until 30 days after the end of participation in the study. During the study, data on SAEs will be collected spontaneously through patient reports, actively elicited during visits through open-ended questioning and examination, and gathered at the time of telephone contact and medical record reviews during the follow-up period. If a patient receives care at a non-VA facility for a SAE they experience, research personnel will obtain the requisite release of information form(s) from the patient and once received, acquire the pertinent medical records from the facility.

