If the toxicity is severe enough to require removal of the patient from the study and the blind is broken, the participant and physician will be informed of the drug they were receiving.

XVII. Data Management and Data Security Plans

The Boston CSPCC will manage the trial data using a web-based Electronic Data Capture (EDC) system. The EDC system allows direct entry of case report forms (CRF) into a web-based study database and thus allows site coordinators to manage their participants, handle data clarifications, and correct data online. This system makes patient data management easier, timelier, and more efficient. The electronic system will be used to create, modify, maintain and retrieve clinical data for CSP#594 during each step of the data collection process. The EDC system will be validated by the Boston CSPCC Quality Assurance department to ensure the integrity of the data capture software.

Paper CRFs for all data including Quality of Life measures will be provided to site coordinators as a primary means of collecting data. Data entered on paper CRFs will be used as source documentation for EDC entries. All paper-based study records will be kept under lock and key.

The Study Chair and Study Director will prepare an Operations Manual. A training session at the study kick-off meeting for all site investigators and site coordinators will be conducted to assure uniformity in patient management, data collection, and study procedures. At this training, site coordinators will be provided with reference materials on the software tool and tasks. Formal training on the use of the EDC system for clinical study management will also be conducted at investigator meetings and on an as-needed basis for new study personnel.

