**Table A6. Early Terminations**

Reason for Termination	Sample (N= )	Form Location	Element Codes
Death	N (%)	EOS	DSDECOD=1
Side effects with study medications	N (%)	EOS	DSDECOD=2
Provider decision	N (%)	EOS	DSDECOD=3
Participant decision	N (%)	EOS	DSDECOD=4
Participant lost to follow-up	N (%)	EOS	DSDECOD=5
Study site closure	N (%)	EOS	DSDECOD=6
Participant required to take exclusion medication on a regular basis	N (%)	EOS	DSDECOD=7
Other reasons for early termination	N (%)	EOS	DSDECOD=8

See Appendix C.

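### The documents conflict on whether reasons other than the patient's own decision end study participation, and no passage clearly provides for Phase 3 flare collection after such an early termination.

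*SAP*

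**What the plan says.** Some passages keep participants in the study when treatment fails or stops.

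- Protocol VIII, Sample Size and Statistical Power: non-adherence, missing the urate target and missed visits do not create dropout; "only the explicit decision of the patient to leave the study" does. The same section says that Phase 3 adverse events lead to treatment adjustment and not to dropout.
- Protocol VII, secondary end point 7: participants meeting the hypersensitivity criteria "will discontinue study medication and will be counted as a treatment failure but will continue to be followed".

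Others allow participation to end for other reasons.

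- SAP 7, Table A6 (Early Terminations) gives End of Study codes for "Side effects with study medications", for provider decision and for "Participant required to take exclusion medication on a regular basis". Participant decision has its own code.
- Protocol XVI, Authorization to Break the Blind: "If the toxicity is severe enough to require removal of the patient from the study and the blind is broken".
- Protocol XVIII, Protocol deviations: a participant with repeated violations may be recommended for termination, and one may be withdrawn for his or her own welfare after consultation.
- Protocol VII, secondary end point 7: after a cardiovascular event, the site investigator decides whether the participant continues in the protocol.

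Four provisions bear on data after an early exit.

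- Table 5, footnote 4 requests one closing visit if feasible: week 48 for those in Phase 1 or 2, week 72 for those in Phase 3.
- Protocol VIII offers chart review for Phase 3 flares, with permission, to people who leave follow-up procedures but remain on study.
- Protocol XVI: "SAEs will be collected from the time of consent until 30 days after the end of participation in the study".
- Protocol XI, Post Study Care: for those who withdraw early or are lost, "the study team will unblind them at what would have been their expected week 72 visit", by a letter to the primary care provider and a chart note. No outcome is recorded at that point.

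**The concern.** Stopping study drug and leaving the study are different events, and the documents do not keep them apart. A site could follow a hypersensitivity case to week 72 and, under the same plan, close out a participant who stopped for another side effect or at a provider's decision. These events occur after randomisation and may differ by arm.

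SAP 3.3 expects participants with severe side effects to leave during Phases 1 and 2, then promises an ITT re-analysis to see whether that dropout changes the comparison. The protocol also calls its primary analysis intent-to-treat. Both need Phase 3 flare outcomes from these people, and outcomes that are never collected cannot be recovered at the analysis stage. Mortality, which the protocol singles out for emphasis, has a similar gap.

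**Working it through.** **1. The plan's own figures.** With unpooled variance, a true difference of 0, a margin of 0.08 and one-sided 5%, power = Φ(0.08 / √(2p(1−p)/n) − 1.645). At 450 per arm and p = 15%, 20% and 25% this gives 95.7%, 91.2% and 87.0%; Protocol VIII states 96%, 91% and 87%. At 425 per arm and p = 20% it gives 89.8%; SAP 4 states 90%. At 15% attrition (950 × 0.85 = 807.5 retained) it gives 88.4%. Lost numbers alone therefore cost little power. The issue is selective loss.

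**2. What is provided for someone terminated in Phase 1 or 2.**
- The closing visit is the week-48 visit. Phase 3 covers weeks 49 to 72, so this visit yields no Phase 3 flare data.
- The chart review is described for people still on study, within a discussion of Phase 3 dropout. It needs permission, and the SAP does not mention it.
- The worst-case and best-case analyses in SAP 5.4.1 cover only the Primary Analysis cohort, which SAP 5.4 limits to those on study when Phase 3 begins.
- Table A7 lists no separate form for permanently stopping study drug, although the dosage-change form might record it.

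**3. How many people.** The protocol allows 5% dropout in the power section and up to 15% attrition under Missing Data. It attributes 3 of the 5 annual dropout points in Phases 1 and 2 to side effects or reluctance to titrate. Applying that 3-in-5 share across the range:
- 0.6 × 0.05 × 950 = 28.5, about 29 people (3%)
- 0.6 × 0.15 × 950 = 85.5, about 86 people (9%)

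**4. Person-years outside the safety data.** Planned: 950 × 72/52 = 1,315. Assume exit at week 24 on average, plus 30 days (4.3 weeks) of SAE collection. Each leaver then loses (72 − 24 − 4.3)/52 = 0.84 person-years.
- 28.5 × 0.84 = 24, and 24/1,315 = 1.8%
- 85.5 × 0.84 = 72, and 72/1,315 = 5.5%

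**5. Unseen flare difference.** Let p be the flare risk in those retained and q the risk in those terminated, each the same in both arms. Let m_A and m_F be the termination proportions. The all-randomised difference that goes unseen is (m_A − m_F)(q − p). The termination rates and q are assumptions, not figures from the documents; p = 20% is the planning rate.
- 8% v 5%, q = 50%: 0.03 × 0.30 = 0.9 points
- 12% v 5%, q = 60%: 0.07 × 0.40 = 2.8 points
- Equal terminations and equal risks: 0
- Rates reversed between arms: the same size with the opposite sign

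The assumed rates average 6.5% and 8.5% across arms, inside the 3% to 9% of step 3 but in its upper part. For scale, an observed difference can reach 8 − 1.645 × 100 × √(0.32/n) points before the bound is crossed: 3.6 at 450 per arm and 3.5 at 425.

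**The case against.** The strongest defence is that the passages can largely be read together. The power section defines dropout; it does not state a rule for follow-up. Table A6 stands among DMC table shells marked as subject to change, and it tabulates reasons without ordering anyone's removal. A side-effect code may simply record why a patient chose to leave. The excluded-medication reason appears only there, and Table A5 treats taking such a medication as a protocol deviation. The unblinding passage is conditional, and termination for violations follows remedial action.

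Much of this stands, and it limits what can be claimed. A reader might infer that Phase 3 flares and later deaths are not collected for these participants. The documents do not say so. Chart review may reach some of the flares, and consented ten-year record access (Protocol V, Other Objectives) covers mortality, though Protocol XI limits it to VA patients. A reader might also infer that the primary non-inferiority result is exposed to the full 0.9 to 2.8 points. That does not follow under the SAP: Phase 1 and 2 leavers are outside its primary set even with complete data.

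The defence does not remove the conflict. Table A6 cites coded values on the End of Study form and separates these reasons from participant decision. Nothing states what is collected once that form is filed for them.

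**Conclusion.** The conflict is real, and the gap is one of provision. For a participant terminated in Phase 1 or 2 for a reason other than his or her own decision, neither document clearly provides for Phase 3 flare collection. The SAP's ITT re-analysis and the protocol's intent-to-treat comparison would lack those outcomes. Deaths more than 30 days after participation ends are outside the trial safety data, and record access recovers them only for consenting VA participants, not for RAIN participants.

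The size is about 29 to 86 of 950 people and about 2% to 5.5% of planned person-years. Both are upper readings: the 3-in-5 share includes patients who chose to leave, and record access would restore part of the person-time. The flare difference of 0.9 to 2.8 points rests on assumed unequal terminations and higher flare risk among leavers, and vanishes if both are equal across arms. This is a modest, inexpensive improvement; it does not show that the primary test is invalid.

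**What to change.** Leave every decision on stopping study drug as it is. Reconcile Protocol VII (secondary end point 7), VIII (dropout and chart review), XVI (removal for toxicity) and XVIII (termination and withdrawal) with SAP Table A6, and state what is collected after each kind of exit.

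Then:
- Record stopping study drug separately from ending study participation.
- Keep consenting participants who stop drug in the Phase 3 flare calls already scheduled, or in the chart review if they decline calls.
- Extend the week-72 contact in Protocol XI to all early terminations who have not revoked consent or HIPAA authorization, and record vital status and date of death there.

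The cost is protocol and case report form wording, plus some site time for calls and chart review. The week-72 contact is now an outgoing letter and a chart note, so recording outcomes is new work, and more of it at RAIN sites. Some participants will still decline.

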**Table A7. Form Completion, by Form Type**

Form Name	#Forms Expected	#Forms Completed
Adverse Event Follow Up	N	N (%)
Adverse Event	N	N (%)
Alcohol Use Questionnaire	N	N (%)
Change in Study Medication Dosage	N	N (%)
Clinical Biochemistry Laboratory Test	N	N (%)
Concomitant Medications	N	N (%)
Demographics	N	N (%)
Eligibility and Randomization	N	N (%)
End of Study	N	N (%)
EQ5D-3L	N	N (%)
Gout Attack Diary and Questionnaire	N	N (%)
Index Tophus Location and Area	N	N (%)
Military History	N	N (%)
Participant Contact Information	N	N (%)
Protocol Deviation	N	N (%)
Rash Adverse Event Form	N	N (%)
Relevant Medical History	N	N (%)
Serious Adverse Event Follow Up	N	N (%)
Serious Adverse Event	N	N (%)
Study Medication Adherence	N	N (%)
sUA unscheduled	N	N (%)
Vital Signs	N	N (%)
VR-12	N	N (%)

\*Expectation: >=90% submission

**Table B1. Patient Characteristics**

Characteristic	Sample VA (N= )	Sample RAIN (N= )	Form Location	Element Codes
Age (years)				
Mean ± SD	Mean ± SD	Mean ± SD	Eligibility and Demographics	Average, Stddev ( floor(Randdt-Brthdat)/365.25)
Range	(Range)	(Range)	Eligibility and Demographics	Range=(min-max(Randdt-Birthdat))
Sex				
Male	N (%)	N (%)	Demographics	SEX = 1
Female	N (%)	N (%)	Demographics	SEX = 2
Race				
American Indian/Alaskan Native	N (%)	N (%)	Demographics	RaceAI = 1
Asian	N (%)	N (%)	Demographics	RaceAs = 1
Black/African American	N (%)	N (%)	Demographics	RaceAA=1
Native Hawaii/Pacific Islander	N (%)	N (%)	Demographics	RacePI=1
White / Caucasian	N (%)	N (%)	Demographics	RaceW=1
Other / Multiple Selected	N (%)	N (%)	Demographics	RaceO=1
Ethnicity				
Not Hispanic or Latino	N (%)	N (%)	Demographics	Ethnic=1
Hispanic or Latino	N (%)	N (%)	Demographics	Ethnic =2
Participant chose not to answer	N (%)	N (%)	Demographics	Ethnic =-99
Education				
Less than High School Diploma	N (%)	N (%)	Demographics	Educatn = 1
High School Diploma	N (%)	N (%)	Demographics	Educatn = 2
Some College credit but no Degree	N (%)	N (%)	Demographics	Educatn = 3
Associate's Degree	N (%)	N (%)	Demographics	Educatn = 4
Bachelor's Degree	N (%)	N (%)	Demographics	Educatn = 5
Master's Degree	N (%)	N (%)	Demographics	Educatn = 6
Doctoral Degree	N (%)	N (%)	Demographics	Educatn = 7
Other	N (%)	N (%)	Demographics	Educatn = 8
Marital Status				
Married	N (%)	N (%)	Demographics	Marital=1

Divorced	N (%)	N (%)	Demographics	Marital=2
Civil Commitment	N (%)	N (%)	Demographics	Marital=3
Never Married	N (%)	N (%)	Demographics	Marital=4
Widowed	N (%)	N (%)	Demographics	Marital=5
Separated	N (%)	N (%)	Demographics	Marital=6
Cohabiting	N (%)	N (%)	Demographics	Marital=7

**Table B2. Military Service, VA sites only**

Characteristic	Sample* (N=)	Form Location	Element Codes
Military Service			
Army	N (%)	Military History	MilBranchA =1
Navy	N (%)	Military History	MilBranchN =1
Air Force	N (%)	Military History	MilBranchAF =1
Marine Corps	N (%)	Military History	MilBranchM =1
Coast Guard	N (%)	Military History	MilBranchCG =1
Other	N (%)	Military History	MilBranchOth =1
Service Periods			
Prior to World War II (Nov 1941 or earlier)	N (%)	Military History	MilWartimePWW =1
World War II Era (Dec 1941-Dec 1946)	N (%)	Military History	MilWartimeWW =1
Jan 1947-June 1950	N (%)	Military History	MilWartime47 =1
Korean Conflict Era (July 1950-Jan 1955)	N (%)	Military History	MilWartimeK =1
Feb 1955-July 1964	N (%)	Military History	MilWartime55 =1
Vietnam Conflict Era (Aug 1964-April 1975)	N (%)	Military History	MilWartimeV =1
May 1975-July 1990	N (%)	Military History	MilWartime75 =1
Persian Gulf War Era(Aug 1990-Feb 1991)	N (%)	Military History	MilWartimePG =1
March 1991-Sep 2001	N (%)	Military History	MilWartime91 =1
Afghanistan/Iraq Conflict Era (Oct 2001-Present)	N (%)	Military History	MilWartimeAI =1

\*Number of subjects from VA sites only

